## 1. PROTOCOL SYNOPSIS

**TITLE:** A Randomized Open Label Phase 2b/3 Study of the Safety and Efficacy of NP-120 (Ifenprodil) for the Treatment of Hospitalized Patients with Confirmed COVID-19 Disease

**TRIAL DESIGN:** Open-label, multi-center, randomized, parallel group study

This protocol is largely based on the recommendations of the [WHO R&D Blueprint Clinical Trials Expert Group COVID-19 Therapeutic Trial Synopsis](#), and associated [Master Protocol](#).

**NUMBER OF STUDY CENTERS:** Approximately 10

**STUDY LOCATION:** Canada, US, Australia, Philippines, Romania

**PHASE OF DEVELOPMENT:** 2b/3

**INDICATION:** Treatment of SARS-CoV-2 Infected Patients

**INVESTIGATIONAL PRODUCT:** NP-120 (Ifenprodil tartrate)

**STUDY RATIONALE:** NP-120 (Ifenprodil) is an N-methyl-D-Aspartate (NDMA) inhibitor that is specific for the NR2B subunit of the NMDA Receptor. The NMDA receptor, and specifically the NR2B subunit, is involved in glutamate signaling, and is expressed on both neutrophils and T cells. In the case of neutrophils, activation of the NMDA receptor can (1) result in expression of CD11b which targets neutrophils via ICAM-1 to areas of inflammation, and (2) trigger the autocrine release of glutamate. In the case of T-cells, activation of T cells via glutamate can cause (1) T cell proliferation and, (2) the release of cytokines. The activation of T cells and cytokine release can be blocked *in vitro* by the addition of Ifenprodil. As such it could be a potent anti-inflammatory agent.

Ifenprodil was discovered by a genome wide RNAi assay to uncover gene targets associated with cytoprotective activity against highly pathogenic H5N1 influenza, specifically by preserving cell viability *in vitro*. When tested in a murine model of H5N1, the drug at clinically relevant doses: (1) improved survivability from 0% at day 6 to 40% day 14 post-infection, (2) the drug significantly reduced edema and lung injury score and (3) reduced infiltrating T cells, neutrophils and NK cells and attenuated the ‘cytokine storm’. The mortality rate of H5N1 in humans is >50%, whereas the mortality rate of SARS-CoV-2 infected patients is < 5%, and both viruses cause acute lung injury and share similar pulmonary pathologies. NP-120 has also been shown to mediate anti-inflammatory responses and reduce pulmonary fibrosis in a murine model of idiopathic pulmonary fibrosis, a complication which can occur after a respiratory virus infection.

Based on the fact that H5N1 has a significantly higher mortality rate than SARS-CoV-2 but still shares similar lung pathologies, Algenon Pharmaceuticals believes Ifenprodil could reduce lung injury associated with COVID-19 disease, thereby improving lung function and accelerating patient recovery.

The purpose of this Phase 2b/3 trial is to determine the safety and efficacy of NP-120 in the treatment of COVID-19 disease.

**PRIMARY OBJECTIVES:** To investigate the clinical efficacy and safety of NP-120 (20 and 40 mg TID) compared to standard of care in patients hospitalized with COVID-19 disease.

- The choice of the primary outcome measure for Phase 3 will be determined by a pilot Phase 2b study of the first 150 subjects.

- Subject clinical status (on the [WHO7-point ordinal scale](#)) at day 15 is the default primary endpoint

**SECONDARY OBJECTIVES:** To investigate the clinical efficacy of NP-120 (20 and 40 mg TID) as compared to the control arm as assessed by:

- **Ordinal scale:**
  - Time to an improvement of one category from baseline on an ordinal scale.
  - Subject clinical status on an ordinal scale at days 3, 5, 8, 11, and 29.
  - Mean change in the ranking on an ordinal scale from baseline to days 3, 5, 8, 11, 15 and 29 from baseline
- **National Early Warning Score (NEWS):**
  - The time to discharge or to a NEWS of  $\leq 2$  and maintained for 24 hours, whichever occurs first.
  - Change from baseline to days 3, 5, 8, 11, 15, and 29 in NEWS
- **Oxygenation:**
  - Oxygenation free days in the first 28 days (to day 29)
  - Effect on the rate of change of partial pressure of oxygen (PaO2) and PaO2/FiO2 ratio taken at baseline and measured once daily up to 2 weeks of treatment in IP versus control group patients
- **Mechanical Ventilation:**
  - Ventilator free days in the first 28 days (to day 29)
  - Incidence and duration of new mechanical ventilation use during the trial
- **Hospitalization:**
  - Duration of hospitalization (days)
  - Time to discharge (days)
- **Mortality:**
  - 15-day mortality
  - 28-day mortality

**EXPLORATORY OBJECTIVES:** To investigate the effects of NP-120 (20 and 40 mg TID) on lung function, health status, and SARS-CoV-2 RNA status in hospitalized patients with COVID-19 disease.

**SAFETY OBJECTIVES:** To study the safety of NP-120 (20 and 40 mg TID) in hospitalized patients with COVID-19 disease.

**PATIENT POPULATION:** Individuals with COVID-19 disease that are currently hospitalized, and either requiring supplemental oxygen, or non-invasive ventilation or high flow oxygen devices. This corresponds to a score of 4 or 5 (moderate and severe disease) on the WHO proposed ordinal scale for clinical improvement.

**STUDY CONDUCT:** The trial will be conducted in two stages:

1. A Pilot Stage (Phase 2b) and,
2. A Pivotal stage (Phase 3)

**NUMBER OF SUBJECTS FOR THE PILOT STAGE OF THE STUDY:** Approximately 150:

Treatment Arm A: Ifenprodil (20 mg TID) on top of Standard of Care (N=50)  
Treatment Arm B: Ifenprodil (40 mg TID) on top of Standard of Care (N=50)  
Control Arm: Standard of Care (N=50)

For the pilot phase, a sample of approximately 150 patients (50 in Arm A, Arm B and SOC) will be recruited. To account for drop out of 10%, a total of 168 patients will be enrolled.

**NUMBER OF SUBJECTS FOR THE PIVOTAL PHASE 3 STAGE OF THE STUDY:**

For the pivotal phase, a sample of 462 patients (231 in the SOC group and 231 in the active treatment group/s) achieves 90% power to detect a change in the log odds ratio of 0.5596 when the significance level (alpha) is 0.05 using a two-sided test. A log odds ratio of 0.5596 corresponds to an odds ratio of 1.75 comparing treatment to SOC. To account for drop out of 10%, a total of 514 patients will be enrolled.

**Phase 2b Interim analysis and increasing the patient number:** An interim analysis will be conducted on the ITT population when 75 patients complete the clinical status assessment at day 15 (the primary endpoint). A preliminary full analysis report of 150 patients with up to Day 29 entered will also be presented. An interim analysis that allows stopping for futility or efficacy will be considered for Phase 3. Details for the Phase 3 futility or efficacy analysis will be specified in the Phase 3 Statistical Analysis Plan and DSMB Charter as appropriate.

**PRIMARY EFFICACY PARAMETER:** Patient clinical status (on the [WHO 7-point ordinal scale](#)) at day 15 in IP versus SOC control group patients:

1. Not hospitalized, no limitations on activities
2. Not hospitalized, limitation on activities
3. Hospitalized, not requiring supplemental oxygen
4. Hospitalized, requiring supplemental oxygen
5. Hospitalized, on non-invasive ventilation or high flow oxygen devices
6. Hospitalized, on invasive mechanical ventilation or ECMO
7. Death

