***Sample size determination:***

For the pilot Phase 2b phase, a sample of 150 patients (50 in Arm A, Arm B and SOC) will be recruited. To account for drop out of 10%, a total of 168 patients will be enrolled.

For the pivotal Phase 3 phase, A sample of 462 patients (231 in the SOC group and 231 in the active treatment group) achieves 90% power to detect a change in the log odds ratio of 0.5596 when the significance level (alpha) is 0.05 using a two-sided test. A log odds ratio of 0.5596 corresponds to an odds ratio of 1.75 comparing treatment to SOC. The sample size was estimated using the *Tests for Two Ordered Categorical Variables* module in [PASS 14](#). To account for drop out of 10%, a total of 514 patients will be enrolled.

The sample size assumes that the distribution of patients on day 15 will be as shown in [Table 2](#), which is scenario 4 in the WHO master protocol (2020) for enrolled patients with moderate to severe disease under an odds ratio of 1.75.

**Table 2 Distribution of Patients Across Outcome Categories at Day 15: SOC (WHO MP Scenario 4) and Treatment (Assuming OR of 1.75)**

Outcome	Percent of Patients	
	SOC	Treatment
7. Death	2	1.0
6. Hospitalized & on mechanical ventilation or ECMO	1	0.6
5. Hospitalized & on non-invasive ventilation or high flow O2	2	1.2
4. Hospitalized & requires supplemental O2	5	3.03
3. Hospitalized not requiring supplemental O2	17	11.45
2. Not hospitalized but limitations on activities	36	31.90
1. Not hospitalized & no limitations on activities	37	50.70

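### The synopsis attaches 90% power to 231 patients in the active *group/s*, but that figure holds only for one comparison of 231 with 231 at two-sided 5%; two doses sharing the 231 and tested separately would each have about 76%, or 66% at 2.5%

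*Protocol*

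**What the plan says.** The Phase 3 size is given four times. The synopsis paragraph on the number of subjects for the pivotal stage reads "a sample of 462 patients (231 in the SOC group and 231 in the active treatment group/s) achieves 90% power to detect" the target effect, "when the significance level (alpha) is 0.05 using a two-sided test". The synopsis paragraph on sample size determination has the singular: "A sample of 462 patients (231 in the SOC group and 231 in the active treatment group) achieves 90% power". Protocol section 10.3 and SAP section 2.5 also use the singular. All four use the same effect: "A log odds ratio of 0.5596 corresponds to an odds ratio of 1.75 comparing treatment to SOC". All four inflate 462 to 514 enrolled for 10% dropout.

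Other statements that bear on the point:

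- The primary objective covers both doses: "To investigate the clinical efficacy and safety of NP-120 (20 and 40 mg TID) compared to standard of care".
- The primary efficacy analysis (synopsis, Statistical Considerations; protocol section 10.9.1) compares the treatment arms with SOC by a proportional odds model at a two-sided 2.5% level. Neither place limits this to Phase 2b or describes a pooled-dose test.
- Protocol section 4.1 describes Phase 3 as drug versus placebo, each on top of standard care. It does not say whether one or two doses go forward, and it leaves the number of patients and the details to an amendment after Phase 2b. Section 4.2 gives about 682 patients in total (168 + 514) and allows adjustment.

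**The concern.** The plural in the synopsis lets the active side consist of more than one group while keeping the total of 462 and the power of 90%. Reading 231 as the size of each active group is ruled out by that total. With two doses the 231 must be divided, and each dose is then compared with control on fewer patients than the power calculation used.

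The documents give no power for that case and no split of the 231. A planner who takes 462, 514 or 682 from this paragraph into a two-dose pivotal stage could assume a 10% chance of missing an effective dose, when the chance for each dose would be well above that. The primary test level adds to the gap, because the power statement uses 5% and the analysis text uses 2.5%.

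**Working it through.** **Inputs.** Log odds ratio θ = ln 1.75 = 0.5596. Category percentages are from the protocol's Table 2, for categories 7 to 1: SOC 2, 1, 2, 5, 17, 36, 37; treatment 1.0, 0.6, 1.2, 3.03, 11.45, 31.90, 50.70. The treatment column adds to 99.88 and was rescaled to 100. The documents name the method by its software module: "The sample size was estimated using the *Tests for Two Ordered Categorical Variables* module in" PASS 14. The standard Whitehead formula for two ordered categorical samples was used here.

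**Formula.** V = n₁n₂ / [3(n₁ + n₂)] × (1 − Σp̄³), where p̄ is the category proportion averaged over the two groups in proportion to their sizes. Power = Φ(θ√V − z), with z = 1.960 at two-sided 5% and 2.241 at two-sided 2.5%.

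**Step 1: the plan's own figure, 231 versus 231.**
- Σp̄³ = 0.1266, so 1 − Σp̄³ = 0.8734.
- V = 38.5 × 0.8734 = 33.62, and θ√V = 0.5596 × 5.799 = 3.245.
- At 5%: Φ(3.245 − 1.960) = Φ(1.285) = 90.1%.
- Required total for 90%: 12 × 10.507 / (0.5596² × 0.8734) = 461, against 462 stated. Dropout: 462/0.9 = 513.3, so 514.

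The stated power, sample size and dropout figure all reproduce for one comparison of 231 with 231.

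**Step 2: the same comparison at 2.5%.** Φ(3.245 − 2.241) = Φ(1.004) = 84.2%.

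**Step 3: two doses sharing 231 evenly, 115.5 each, against 231 controls.**
- Σp̄³ = 0.1171, so 1 − Σp̄³ = 0.8829.
- V = 25.67 × 0.8829 = 22.66, and θ√V = 0.5596 × 4.760 = 2.664.
- At 5%: Φ(0.704) = 75.9%. At 2.5%: Φ(0.423) = 66.4%.

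**Step 4: sensitivity to the split.** With 462 in equal thirds (154 per arm), V = 22.42 and θ√V = 2.650, giving 75.5% and 65.8%. If the 231 were split unevenly, the smaller dose group would have less power than in Step 3.

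**Cross-check.** A simulation of the tie-corrected Wilcoxon test, 20,000 runs per case:

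| Comparison | Formula, 5% | Simulated, 5% | Formula, 2.5% | Simulated, 2.5% |
|---|---|---|---|---|
| 231 vs 231 | 90.1% | 89.9% | 84.2% | 84.0% |
| 115.5 vs 231 (simulated with 115 and 116) | 75.9% | 74.6–75.2% | 66.4% | 64.8–65.6% |
| 154 vs 154 | 75.5% | 75.0% | 65.8% | 65.6% |

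**The case against.** Four arguments weigh against the point.

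- **Pooling keeps the 90%.** If both doses are combined and compared once with control, the comparison is again 231 with 231, and the paragraph speaks of one odds ratio for treatment against SOC. This stands, provided that both doses share the odds ratio of 1.75. A reader might infer that 90% holds only with a single active group; that is too strong. What holds is that it needs a single 231 versus 231 comparison. No pooled test is planned anywhere, so the plural is not explained by one.
- **Phase 3 is not designed yet.** Section 4.1 names only drug and placebo groups, and sections 4.1 and 4.2 defer arms and size. The primary objective covers the whole 2b/3 trial and is already met by the Phase 2b arms. This also stands. A reader might infer that Phase 3 will test both doses and be underpowered; the documents do not say so.
- **The dose-by-dose test at p < 0.025 in SAP section 11.1 belongs to Phase 2b.** SAP section 1 limits that document to Phase 2b, so the rule cannot be read as a Phase 3 commitment. But the protocol's own primary analysis text states the 2.5% level for the treatment arms without limiting it to one stage.
- **Power per dose is only one definition.** With both doses at odds ratio 1.75 and 115.5 each, the chance that at least one succeeds is about 91% at 5% each and 84% at 2.5% each (correlation 115.5/346.5 = 1/3 between the two tests). The 91% comes without any adjustment for testing twice. The paragraph does not define power as at least one success, and its calculation is for a single comparison.

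**Conclusion.** The point holds as a misattached power figure. The sample size arithmetic is correct: 462 patients give 90% power for one comparison of 231 with 231 at two-sided 5%. The synopsis should not attach that figure to one or more active groups, because it is not the power of each comparison when there are two.

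Under three assumptions (both doses enter Phase 3, each is tested separately against control, and they share the 231 evenly), power per dose is about 76% at 5% and 66% at 2.5%. The chance of missing an effective dose is then about 24% or 34% instead of 10%. The documents state none of these assumptions, so these are conditional figures and not a forecast for the trial.

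Part of the fall to 66% does not come from the plural. One comparison of 231 with 231 has about 84% at the 2.5% level, and this gap between the power statement and the analysis text is present in all four places. Because the Phase 3 size is provisional, the point calls for a correction of wording now. It is not evidence that the pivotal stage is too small.

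**What to change.** In the synopsis paragraph on the pivotal-stage number of subjects, delete the `/s` so that it agrees with the synopsis sample size paragraph, protocol section 10.3 and SAP section 2.5. Then add, for example:

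*The 90% refers to one comparison of 231 active with 231 control patients at two-sided 5%; at two-sided 2.5% the same comparison has about 84% power. If two doses are tested separately against control and the 231 active patients are split evenly between them, power per dose is about 76% at 5% or 66% at 2.5%. The calculation will be repeated in the Phase 3 amendment for the arms and significance level chosen.*

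Sections 4.1 and 4.2 already foresee that amendment, so the last sentence adds only what it must cover. The cost is a short wording change and a less favourable figure for the two-dose case. It adds no patients and does not alter the design.

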**SECONDARY EFFICACY PARAMETERS:**

- Status on an ordinal scale assessed daily while hospitalized and on days 15 and 28 in IP versus control group patients
- NEWS assessed days 3, 5, 8, 11 while hospitalized and on days 15 and 29 in IP versus control group patients
- Rate of mechanical ventilation in IP versus control group patients
- Duration of mechanical ventilation (if applicable) in IP versus control group patients
- Duration of supplemental oxygen in IP versus control group patients
- Time to return to SpO2 > 94% on room air
- Duration in ICU (if applicable) in IP versus control group patients
- Rate of Mortality in IP versus control group patients
- Duration of hospitalization in IP versus control group patients
- Time to discharge in IP versus control group patients

- Effect on the rate of change of partial pressure of oxygen (PaO2) and PaO2/FiO2 ratio taken at baseline and measured once daily up to 2 weeks of treatment in IP versus control group patients

**EXPLORATORY EFFICACY PARAMETERS:**

- Changes in the extent of dyspnea from baseline, using a Likert scale, at Days 2, 4, 8, and 14 in IP versus control group  
[Likert scale: The patient grades his/her current breathing compared to when he/she first started the study (from -3 to 3). "0" = no change, "1" = minimally better, "2" = moderately better, "3" = markedly better, "-1" = minimally worse, "-2" = moderately worse, "-3" = markedly worse]. For the first questionnaire (at baseline), the patient compares their current shortness of breath to their shortness of breath when they are well.
- Rate of change to patient's experience of cough (Visual analog scale [VAS]) at Days 2, 4, 8, and 14 in IP versus control group  
VAS: The patient draws a vertical line on an axial graph (from 0 to 100) to show the degree of how he/she feels about coughing. The number "100" equals the worst coughing the patient has ever felt and the number "0" equals the best he/she has felt since baseline.
- Changes in D-dimer in IP versus control group
- Qualitative PCR for SARS-CoV-2 at baseline, days 5 (while hospitalized, and days 15 and 29 (if able to return to clinic or still hospitalized)
- Quantitative PCR (if available) for SARS-CoV-2 at baseline, days 5 (while hospitalized, and days 15 and 29 (if able to return to clinic or still hospitalized)

**SAFETY PARAMETERS:**

- Type, frequency, severity, and relationship of AEs to investigational product (IP)
- Number of patients who discontinue IP due to any AE
- Frequency of clinically significant changes in vital signs and/or laboratory findings

**TREATMENT:** Test Product: NP-120, 20 or 40 mg TID for up to 2 weeks (either to hospital discharge, or Day 14, whichever comes first). Patients who find it difficult to swallow pills can be administered crushed pills of NP-120 and fed via a naso-gastric tube.

***Duration of subject participation:*** Up to 60 days (from screening to follow up on day 60 ± 3 days)

**INCLUSION CRITERIA:**

1. Male and female subjects aged ≥18 years of age
2. Confirmed coronavirus infection
  - a) Positive real-time fluorescence polymerase chain reaction of the patient's respiratory or blood specimens for SARS-CoV-2 nucleic acid
  - b) Viral gene sequences in respiratory or blood specimens that are highly homologous to SARS-CoV-2
  - c) Any other diagnostic test accepted by local regulatory authorities
3. Must be hospitalized and requiring supplemental oxygen, or on non-invasive ventilation or high flow oxygen devices (Score of 4 or 5 on WHO Ordinal Clinical Scale)
4. Female subjects of childbearing potential who are sexually active with a non-sterilized male partner must use at least 1 highly effective method of contraception (e.g. oral contraceptives,

- intrauterine device, diaphragm plus spermicide) from the time of screening and must agree to continue using such precautions for 90 days after the final dose of study drug(s)
5. Non-sterilized males who are sexually active with a female partner of childbearing potential must use condom plus spermicide from day 1 through 90 days after receipt of the last dose of study drug(s)
  6. Subjects (or legal designate) must have the capacity to understand, sign and date a written, informed consent form and any required authorization prior to initiation of any study procedures

**EXCLUSION CRITERIA:**

1. Patients with vasodilatory shock, orthostatic hypotension, hypotension, or tachycardia at screening/baseline
2. Patients experiencing cerebral hemorrhage or cerebral infarction at baseline
3. ALT/AST > 5 times the upper limit of normal; Child-Pugh Score 10 to 15.
4. Stage 4 severe chronic kidney disease or requiring dialysis (i.e. eGFR < 30)
5. Patients on mechanical ventilation or extracorporeal membrane oxygenation (ECMO)
6. Patients taking droxidopa
7. Pregnant and lactating women and those planning to get pregnant
8. Known or suspected allergy to the trial drug or the relevant drugs given in the trial
9. Presence of other disease that may interfere with testing procedures or in the judgement of the Investigator may interfere with trial participation or may put the patient at risk when participating in this trial
10. Know inability of patient to comply with the protocol for the duration of the study
11. Involvement in a clinical research study within 4 weeks prior to screening and/or prior enrollment in the study or plan to participate in another interventional clinical trial during the study period. Participation in observational registry studies is permitted.

**Schedule of Events:**

Visit	Procedures
Visit 1 (Screening/Baseline/Randomization, Days -1 to 1)	Informed Consent Inclusion/Exclusion Criteria SARS-CoV-2 RNA status testing Pregnancy test Demographics/medical history Vital signs (including SpO2) Physical Exam Clinical support data collection Safety laboratory testing Child-Pugh Score Cytokine Markers PaO2 and PaO2/FiO2 ratio ECG VAS Extent of Dyspnea (Likert Scale) Concomitant medications Randomization Administer IP
Daily until hospital discharge or Visit 2 (Day 15)	Vital signs (including SpO2) Clinical support data collection

	
SARS-CoV-2 RNA status testing (Day 5 or discharge, whichever comes first)                  Safety laboratory testing (Days 3, 5, 8, 11 if hospitalized)                  Child-Pugh Score (Days 3, 5, 8, 11 if hospitalized)                  Cytokine Markers                  PaO2 and PaO2/FiO2 ratio                  VAS (Days 2, 4, 8, and 14 if hospitalized)                  Extent of Dyspnea (Likert Scale, Days 2, 4, 8, and 14 if hospitalized)                  AEs recorded                  Concomitant medications                  IP administration (daily to discharge or Day 14)

Visit 2 – Day 15 (± 2 days)	
Vital signs (including SpO2)                  Clinical support data collection                  SARS-CoV-2 RNA status testing                  Cytokine Markers                  Safety laboratory testing                  PaO2 and PaO2/FiO2 ratio                  VAS                  Extent of Dyspnea (Likert Scale)                  AEs recorded                  Concomitant medications

Visit 3 – Day 29 (± 2 days) Safety Follow Up Visit	
Vital signs (including SpO2)                  Clinical support data collection                  SARS-CoV-2 RNA status testing (if viral RNA still detected on Day 15)                  Safety laboratory testing                  PaO2 and PaO2/FiO2 ratio                  VAS                  Extent of Dyspnea (Likert Scale)                  AEs recorded                  Concomitant medications

Visit 4 – Day 60 (± 3 days)	
Vital Status                  AEs recorded

